Official title: Treatment of acute exacerbations of chronic obstructive pulmonary disease with acupuncture during hospitalization: a three-arm double-blinded randomized sham-controlled trial

NCT number: NCT03398213

Date of the document: June 3, 2020

Methods:

Study design: This is a three-arm 1:1:1 randomized-controlled trial evaluating the efficacy and safety of the addition of acupuncture to SOC as compared to sham-procedure added to SOC (sham-control) and to SOC only (SOC-control) for treatment of AECOPD in patients hospitalized in internal medicine departments. The study protocol was reviewed and approved by the Institutional Review Board (IRB) in accordance with the Helsinki Declaration (0108-17-BNZ) and registered at www.clinicaltrials.gov (NCT03398213). Trial methods and results were reported according to the Consolidated Standards of Reporting Trials (CONSORT) 2010 guidelines.¹⁹

Participants: Patients hospitalized in internal medicine departments with a previous diagnosis of COPD³ were evaluated by department physicians. Inclusion criteria included a previous diagnosis of COPD and a clinical diagnosis of AECOPD as defined by the GOLD criteria.³ Exclusion criteria included hemodynamic instability, a platelet count below $20 \times 10^9/L$, expected respiratory deterioration requiring mechanical ventilation in the next 24 hours, or an inability to provide informed consent. Primary socio-demographic and medical data were recorded and compared between the three study groups.

Setting: The study was set in internal medicine departments of Bnai Zion medical center, a tertiary hospital in Haifa, Israel.

Interventions: The intervention protocol was based on a literature review and the Delphi process. A panel of eight acupuncturists of at least 5 years of experience in treating hospitalized patients were consulted. The experts were asked to review and analyze the literature regarding Traditional Chinese Medicine (TCM) and COPD, delineate relevant TCM syndromes and associated "critical" acupoints and treatment frequency. Their suggestions were based on literature data and their professional experience. Finally, three cycles of stepwise anonymous discussions were taken to obtain a consensus on the treatment approach. The conclusion was to

assign the patients into three groups for four daily consecutive treatment sessions and a 4-day follow-up.

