they were taught they are actually treating patients by stimulating ear acupoints and that the aim of the study was to compare the efficacy and safety of acupuncture administered by an experienced acupuncturist as compared to acupressure administered by unexperienced medical staff after a short training. Patients were told they are receiving ear-point stimulation. Therefore, this study arm was double blinded. SOC was administered as well as described earlier.

Outcomes:

The primary outcome was dyspnea intensity pre- and post-treatment in the 4 days of follow-up. It was measured daily, before and one hour after treatment (for acupuncture and sham-control groups) or after first evaluation (for SOC-control group), via the modified Borg (mBorg) scale, which is a validated scale that has been used to evaluate the degree of dyspnea (0- no dyspnea, to 10- worse dyspnea) in both stable COPD and AECOPD.^{21,22} Dyspnea intensity was chosen as primary outcome since it has been shown to predict clinical outcomes in AECOPD.²³

Secondary outcomes included:

Variation of clinical symptoms: Including cough intensity and sputum production associated with the AECOPD, as evaluated on a Visual Assessment Scale from 0 (no symptom) to 10 (maximally symptomatic), throughout the 4 days of evaluation.

Variation of physiologic features: Venous blood gases (pH and pCO₂) and oxygen saturation were measured before intervention and daily in the four evaluation days. Respiratory rate (RR) was measured daily, before and one hour after treatment (for true acupuncture and sham-control groups) or after first evaluation (for SOC-control group).

Treatment failure: Defined as death during hospitalization or need for noninvasive or mechanical ventilation. Treatment failure incidence was evaluated and compared between the three groups.

Duration of hospitalization: Evaluated and compared between the three study arms.

Safety: Acupuncture-related side effects were systematically evaluated after treatment in the true acupuncture group via the validated Acup-AE questionnaire administered to the patient by the acupuncturist immediately after therapy.²⁴

Minimal sample size: In a previous study evaluating the efficacy of acupuncture vs sham-acupuncture in 68 patients with chronic COPD (34 patients in each group), a 3.6±1.9 units improvement in dyspnea (according to mBorg scale) was found in the acupuncture arm, as

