compared with a 0.4 ± 1.2 units improvement in the sham-acupuncture arm.⁸ According to these data and ANOVA test with alpha of 0.05 and an 80% power, we calculated a minimal sample size of 66 patients (22 in each group) for the current study.

Randomization: Patients meeting inclusion/exclusion criteria were randomized to either SOC with acupuncture (true acupuncture), SOC with sham-procedure (sham-control) or SOC only (SOC-control) using 1:1:1 permuted block randomization. The permuted block randomization list was generated by Excel software. To guarantee allocation concealment, randomization was done by an independent research assistant who did not participate in any other parts of the research and assigned the group code to each participant according to the randomization list. The independent research assistant was blinded to the meaning of the group code.

Blinding: Data collectors, department physicians, physicians administering the sham-procedure and the statistician were blinded to the group allocation status; acupuncturist blinding is clearly not possible, however, contact time with patients was the same in both true acupuncture and sham-control arms (15-20 min). Patients receiving both true acupuncture and sham-procedure were told they are treated for their respiratory condition by acupuncture/acupressure. The group allocation status was revealed after completion of the study.

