- *Treatment failure:*

No death or mechanical ventilation occurred in the study participants during follow-up. However there had a total of 4 treatment failures, all of them were non-invasive ventilations, which occurred in 2 (8%) patients in the true acupuncture arm, 1 (4.3%) in the sham-control arm and 1 (5%) in the SOC-control arm ($p=0.83$).

- *Duration of hospitalization:*

No difference was noted in terms of duration of hospitalization between the three study arms (5.5 ± 2.3 days for true acupuncture vs. 6.0 ± 2.9 days for sham-control and 6.3 ± 2.9 days for SOC-control, $p=0.050$).

- *Safety:*

No side effect of acupuncture treatment was reported during the study period as assessed by the Acup-AE questionnaire.

Tables and Figures:

Table 1: Baseline characteristics

[figure not shown]
Characteristics	True acupuncture (N=26)	Sham-control (N=24)	SOC-control (N=22)	p
Age (mean ± SD)	69.2±10.1	70.7±8.1	67.4±9.3	0.47
Gender (Men)	20 (77%)	15 (62%)	17 (77%)	0.43
Comorbidities				
Cardiovascular	18 (69%)	20 (83%)	15 (68%)	0.42
Respiratory (other than COPD)	7 (27%)	2 (8%)	5 (23%)	0.23
Gastroenterological	2 (8%)	4 (17%)	5 (23%)	0.34
Renal / Urologic	7 (27%)	3 (12%)	5 (23%)	0.44
Metabolic / Endocrinological	15 (58%)	13 (54%)	13 (59%)	0.94
Hematological / Oncological	3 (12%)	6 (25%)	3 (14%)	0.40
Neurological	4 (15%)	0 (0%)	1 (5%)	0.09
Smoking status				
Smoker	13 (50%)	16 (67%)	14 (64%)	0.44
Former smoker	13 (50%)	8 (33%)	8 (36%)	
Never smoked	0	0	0	
CCI (median [Q1, Q3])	6.0 [3.5, 6.0]	5.0 [4.0, 6.75]	4.5 [3.0, 7.25]	0.87
COPD severity				
Mild: FEV1 ≥ 80%	1 (4%)	0 (0%)	1 (5%)	
Moderate: 50% ≤ FEV1 < 80%	4 (15%)	5 (21%)	5 (23%)	0.69
Severe: 30% ≤ FEV1 < 50%	7 (27%)	11 (46%)	9 (41%)	
Very severe: FEV1 < 30%	5 (19%)	4 (17%)	4 (18%)	
Unknown	9 (35%)	4 (17%)	3 (14%)	
Pulmonary hypertension				
None	10 (38%)	15 (62%)	16 (73%)	
Mild: mPAP = 25-40 mmHg	4 (15%)	3 (12%)	3 (14%)	
Moderate: mPAP = 41-55 mmHg	3 (12%)	0	2 (9%)	0.11
Severe: mPAP > 55 mmHg	0	0	0	
Unknown	9 (35%)	6 (25%)	1 (5%)	
COPD exacerbation hospitalizations				
0	19 (73%)	12 (50%)	9 (41%)	
1-4	6 (23%)	11 (46%)	9 (41%)	0.09
≥5	1 (4%)	1 (4%)	4 (18%)	
Treatment				
Inhalations	24 (92%)	23 (96%)	22 (100%)	0.41
Systemic corticosteroids	3 (12%)	3 (13%)	1 (5%)	0.61
Theophylline	0	0	1 (5%)	0.32
Oxygen home therapy	8 (31%)	12 (52%)	8 (36%)	0.29
BiPAP	4 (15%)	2 (8%)	4 (18%)	0.60
APACHE-II at admission (mean ± SD)	13.3±3.6	12.0±4.4	11.0±3.8	0.14
Baseline data (median [Q1, Q3])				

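### Side effects are collected only in the acupuncture arm, by the unblinded acupuncturist, so the stated safety comparison with sham and SOC cannot be made for side effects

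*Combined protocol and SAP*

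**What the plan says.** All references are to the combined protocol and SAP.

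- **Study design** sets a comparative aim that covers safety as well as efficacy: "evaluating the efficacy and safety of the addition of acupuncture to SOC as compared to sham-procedure added to SOC (sham-control) and to SOC only".
- **Outcomes, Safety** is the only outcome with that label. It reads "Acupuncture-related side effects were systematically evaluated after treatment in the true acupuncture group", and gives the method as "via the validated Acup-AE questionnaire administered to the patient by the acupuncturist immediately after therapy".
- **Blinding** states that "acupuncturist blinding is clearly not possible". It also states: "Data collectors, department physicians, physicians administering the sham-procedure and the statistician were blinded to the group allocation status".
- **Outcomes, Treatment failure** combines in-hospital death with any ventilatory support and is compared across the three arms. Blood gases, oxygen saturation and respiratory rate are also followed in all arms.
- **Statistical analysis** has no separate safety analysis.
- **Results, Safety** says "No side effect of acupuncture treatment was reported during the study period", citing the Acup-AE questionnaire. It gives no denominator, no confidence limit and no count for sham or SOC.

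**The concern.** An aim worded as a comparison needs the same events sought in the same way in each arm. Here the aim names two comparators, and the side-effect instrument reaches neither. Patients admitted with a COPD exacerbation have many symptoms of their own. Without a control rate, a symptom that arises after needling cannot be separated from the illness or its drugs, and a zero count cannot be set against what plasters or usual care would have shown.

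The method of asking adds a second weakness. The interviewer knows the treatment and, on the natural reading, has just given it. The plan names blinded data collectors but does not use them here. Dyspnea and respiratory rate are measured one hour after treatment, so a later contact existed, yet no side-effect question is described at that contact or after the fourth session.

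At stake is whether the trial can say anything about the safety of acupuncture relative to its controls. The dyspnea result is not affected.

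**Working it through.** **1. Is a side-effect comparison possible?** Set the harm-relevant data side by side.

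| Data | Arms | Assessor | Timing |
|---|---|---|---|
| Acup-AE side effects | acupuncture only | acupuncturist, unblinded | immediately after the session |
| Treatment failure | all three | not stated | during hospitalization |
| Blood gases, saturation | all three | not stated | before intervention, then daily |
| Respiratory rate | all three | not stated | daily, before and one hour after treatment (SOC: after first evaluation) |

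A risk difference or ratio for side effects needs a count and a denominator in at least two arms. Only one arm has them, so neither can be computed.

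**2. The document's own three-arm figure.** Treatment failure is reported as 2, 1 and 1 events, p=0.83. Pearson chi-square with 2 degrees of freedom, where p = exp(−X²/2):

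- denominators 26/24/22 (as randomized): X² = 0.3573, p = 0.836;
- denominators 25/23/22: X² = 0.3779, p = 0.828.

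The stated p is reproduced to within rounding or a small difference in denominators. The sham percentage of 4.3% fits 1/23 better than 1/24 (4.2%), so the denominators should be printed. The comparison exists, but it rests on 4 events, all noninvasive ventilation.

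**3. What the zero can support.** Input: 26 patients in the acupuncture arm (Results, Baseline patient data). Assumption: all 26 answered the questionnaire. The exact upper limit solves (1 − p)^26 = α:

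- two-sided 95%: 1 − 0.025^(1/26) = 0.132, or 13.2%;
- one-sided 95%: 1 − 0.05^(1/26) = 0.109, or 10.9%.

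**4. What three-arm collection would have given.** With zero events in a control arm, the two-sided limits would be 1 − 0.025^(1/24) = 14.2% for sham and 1 − 0.025^(1/22) = 15.4% for SOC. Against a zero control count, Fisher's exact test first falls below 0.05 at 6 of 26 events (p=0.023 against 0/24; p=0.025 against 0/22). The true rates below are assumptions, not in the document. With 26 against 24 patients, power is about 42% for 20% against 0%, and about 19% for 20% against 5%. These figures use an unadjusted 0.05. The plan's Bonferroni adjustment over three pairs (0.05/3 = 0.0167) would lower them.

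**The case against.** **Harm-type outcomes are compared in all three arms.** This is true, and it limits the point. Treatment failure is reported by arm, with no deaths, and the physiologic measures are followed daily. The point therefore covers side effects, the designated Safety outcome, and not every adverse event. Four events make the treatment-failure comparison imprecise, and neither it nor the physiologic data would register pain, bleeding or skin reactions from needles or plasters.

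**An acupuncture questionnaire has no meaning for patients who were not needled.** This stands in part. It explains why this instrument does not suit the SOC arm. It does not explain why no general symptom question was put to all arms, and the sham arm did receive a procedure.

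**The trial is too small to compare side effects.** Power would be low, as shown. That argues for reporting wide intervals, not for having no comparator data.

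**The safety result is worded descriptively.** It is, and no comparative side-effect claim appears in the results. The mismatch is with the stated aim, so for the finished trial the correction is mainly one of wording.

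**The 13.2% limit does not measure the defect.** Agreed. It follows from the arm size and would be the same with a blinded interviewer. It shows how little a zero in 26 excludes; the lack of a comparator and any reporting bias are not quantified.

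**Conclusion.** The concern holds for side effects. The document states a comparative safety aim against sham and SOC, collects its only Safety outcome in the acupuncture arm through an unblinded acupuncturist, and specifies no later side-effect assessment. No between-arm side-effect comparison is possible. The zero excludes per-patient rates above 13.2% (two-sided 95%) and no lower, assuming 26 completed responders and no under-reporting.

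A reader might infer three stronger conclusions that the document does not support:

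- *No safety comparison of any kind can be made.* Treatment failure and the physiologic measures are compared across all arms.
- *Nothing after the end of a session is captured.* Death, ventilation, dyspnea and respiratory rate are recorded later. For side effects, the document does not say whether the questionnaire asks about the time since the previous session, so the supportable statement is only that no later assessment is specified.
- *The zero reflects under-reporting to an interested interviewer.* The document shows an unblinded assessor, which is a route to bias. It shows neither a motive nor missed events. That the interviewer was the person who gave the session is itself a natural inference, not an explicit statement.

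The matter should be corrected because a stated aim is left unsupported. It does not bear on the primary outcome.

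**What to change.** **For the data in hand:**

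- Limit the safety statement to a description of the acupuncture arm. Report 0/26 with its exact two-sided upper limit of 13.2%, or recompute the limit if fewer than 26 patients completed the questionnaire.
- State who asked, when, and how many questionnaires were completed.
- Remove the comparative wording for side effects from Study design.
- Present treatment failure by arm, with denominators, as the only comparative harm-type event outcome.

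This costs a few sentences and one count from existing records.

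**For the plan or any repeat:**

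- At the daily post-treatment contact that already occurs in every arm, ask the same neutrally worded general symptom checklist after dyspnea and respiratory rate have been recorded.
- Keep needle-site items on a separate patient-completed form that the blinded data collectors do not see.
- Report incidence by arm with exact confidence intervals.

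The cost is a few questions per contact and one extra form. The document does not say who takes the dyspnea and respiratory-rate readings, so the task must be assigned explicitly. Some risk of unblinding remains: asking after the ratings protects that day's values, but a symptom volunteered on one day could still reveal the arm before the next day's dyspnea score. Some items will not apply to SOC patients, and intervals will be wide at 22 to 26 patients per arm.

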Standard-of-care (SOC) only: Patients received SOC for AECOPD according to a standard protocol based on the GOLD guidelines.³ Such therapy included oxygen to maintain saturation around 90%, inhalations, antibiotics and systemic corticosteroids for five days. Noninvasive or mechanical ventilation were added depending on the severity of the AECOPD, as determined by clinical evaluation and blood gases.

True acupuncture + SOC group: Acupuncture treatment was documented according to STRICTA guidelines.²⁰

- Acupuncture rationale: The acupuncture was performed in a TCM style. During the Delphi process, a list of acupoints relevant to acute lung conditions were determined and associated with different TCM syndromes. Practitioners systematically documented syndrome diagnosis according to TCM reasoning and used only acupoints appearing in the list and corresponding to the TCM diagnosis.
- Details of needling: During the treatment, the acupuncturists used 75% alcohol pads to sterilize the skin around the acupoints. Subsequently, sterile disposable needles were inserted in the acupoints. An average of five Eco FDA-approved needles of 3-cm length and 0.22-mm diameter were inserted. The puncture depth varied with anatomical location from 0.5 to 1 cm. Manual needle stimulation was performed, but *de qi* sensation (e. g. dullness, sourness, heaviness, tingling sensation around the needle) was not sought.
- Treatment regimen: Four daily consecutive 15-20-minute sessions were administered.
- Other components of treatment: Patients in this group also received SOC as described earlier. No other complementary medicine therapies were added. Explanations were given to patients on potential benefits and side effects of acupuncture and treatment was administered only after they signed informed consent.
- Practitioner background: The treatment was administered by eight acupuncturists with at least 5 years of clinical experience in a hospital setting.
- Control intervention: The two control groups were SOC only (SOC-control) and SOC with sham-procedure (sham-control).

Sham-procedure + SOC group: Department physicians underwent a one-hour training on placing plasters on ear-points that have no relevance to lung conditions. During this training,

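### The double-blind label is too broad: physicians placing the sham plasters knew who was in that arm, and both contrasts with SOC-control are open-label for patients on a patient-rated outcome

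*Combined protocol and SAP*

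**What the plan says.** The combined protocol and SAP describes blinding in four places.

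- **Official title:** "a three-arm double-blinded randomized sham-controlled trial". The label covers all three arms.
- **Blinding section:** "Data collectors, department physicians, physicians administering the sham-procedure and the statistician were blinded to the group allocation status". The same section concedes that acupuncturists could not be blinded, says contact time was equal in the two procedure arms, and adds: "Patients receiving both true acupuncture and sham-procedure were told they are treated for their respiratory condition by acupuncture/acupressure". It says nothing about SOC-control patients.
- **Sham-procedure + SOC group:** "Department physicians underwent a one-hour training on placing plasters on ear-points that have no relevance to lung conditions". On what these physicians believed: "they were taught they are actually treating patients by stimulating ear acupoints". They were also told that the study compared experienced acupuncturists with "acupressure administered by unexperienced medical staff after a short training". The paragraph concludes: "Therefore, this study arm was double blinded". Here the term covers the sham arm only.
- **Control intervention (acupuncture arm description):** one of the two controls is standard of care alone, with no procedure.

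The primary outcome is the mBorg dyspnea score. Its results are shown in Figure 2A, and Figure 2 is titled as a comparison of patient-reported outcomes. The Statistical analysis section names all three pairwise contrasts, with Bonferroni adjustment.

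**The concern.** A reader who meets a double-blind label and a list of blinded parties will credit every contrast with that protection. The arm descriptions do not support this. A physician who places plasters on a patient cannot be unaware that the patient is in the plaster group. A patient who gets neither needles nor plasters cannot be unaware of receiving no procedure.

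This matters because dyspnea, cough and sputum are rated by the patient, and knowing that one is or is not being treated can act on such ratings directly. The contrasts with SOC-control are also prominent in the results. The day-1 post-treatment comparison of acupuncture with SOC-control (p=0.014) is reported beside acupuncture vs sham (p=0.031), and the adjusted model in Table 2 takes SOC-control as its reference. The only adjusted acupuncture effect with an interval is therefore one in which patients were not masked.

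**Working it through.** No formula decides the blinding question. The check is to ask, party by party and contrast by contrast, what each could know. Arm sizes are from Results, Baseline patient data: acupuncture 26, sham 24, SOC-control 22.

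| Party | Acupuncture vs sham (26 + 24 = 50) | Acupuncture vs SOC (26 + 22 = 48) | Sham vs SOC (24 + 22 = 46) |
|---|---|---|---|
| Patients | Know whether they get needles or plasters; masked at most to the plasters being a sham | Open-label | Open-label |
| Physicians placing plasters | Know who is in the plaster group; not told it is inert | Deliver neither; documents silent on what they could tell | Know who is in the plaster group |
| Acupuncturists | Not blinded (conceded) | Not blinded (conceded) | Deliver neither |
| Other department physicians | Stated blinded; method not described | Same | Same |
| Data collectors, statistician | Stated blinded; not contradicted | Same | Same |

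Two separate gaps follow, and they fall on different contrasts. Plaster placement affects the two contrasts that involve sham. The absence of a procedure affects the two that involve SOC-control. Only sham vs SOC is affected by both.

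**What Table 2 gives for the contrast with the most masking.** The outcome is the variation of dyspnea from day 1 to day 2, with SOC-control as reference.

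- Acupuncture vs SOC: 2.172 (95% CI 0.421 to 3.923); half-width (3.923 − 0.421)/2 = 1.751.
- Sham vs SOC: 0.390 (95% CI −1.319 to 2.099); half-width (2.099 + 1.319)/2 = 1.709.
- Acupuncture vs sham, by subtraction: 2.172 − 0.390 = 1.782.

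The interval for 1.782 cannot be derived from the table, because it depends on the unreported correlation r between the two coefficients. Both come from one model, so the half-width is √(1.751² + 1.709² − 2r × 1.751 × 1.709) = √(5.987 − 5.985r). It equals 1.782 when r = (5.987 − 3.176)/5.985 = 0.47. Taking r from 0.3 to 0.7 as an assumption:

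- r = 0.3: half-width 2.047, interval −0.265 to 3.829.
- r = 0.7: half-width 1.341, interval 0.441 to 3.123.

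Whether the adjusted interval excludes zero therefore turns on a figure that the report does not show.

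**The case against.** The best defence is that the body text is more careful than the title. The sham paragraph confines the double-blind term to one arm, the Blinding section concedes that acupuncturists were unblinded, and no sentence in the body claims that SOC-control patients were blinded. That is right. For patients, the conflict is with the title and not with the Blinding section.

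A second defence is that the Blinding section lists department physicians and sham-giving physicians as separate parties, so not every department physician need have placed plasters. This also stands, but it does not remove the contradiction, because the sham-giving physicians are themselves listed as blinded to allocation.

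Four stronger readings are tempting, and the documents do not support them:

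- **That the stated blinding does not exist.** The sentence also names data collectors and the statistician, and nothing contradicts either, although how collectors were kept blind is not described.
- **That treatment failure and length of stay are open-label.** The documents do not say who decided on ventilation or discharge, or what those physicians knew. Neither outcome is claimed as a benefit.
- **That the training script biased acupuncture vs sham.** Physicians were told they were giving real treatment, not that their arm would do worse, and nothing shows that the remark about inexperience reached the patients who rated dyspnea. Bias is possible, not documented.
- **That day-1 medians show how much of the SOC contrast is non-specific.** The sham–SOC gap is 7.5 − 6.0 = 1.5 of the acupuncture–SOC gap of 7.5 − 5.0 = 2.5. But 7.75 − 6.5 = 1.25 of that 1.5 was present at baseline (Table 1). Differences between medians are also not median changes, so these figures do not measure bias from unblinding.

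**Conclusion.** The point holds in a bounded form. The title claims more masking than the design has. The statement that the physicians giving the sham were blinded to allocation conflicts with their own task; they were masked only to its being inert. Two of the three tested contrasts, with 48 and 46 patients, are open-label for patients on a patient-rated primary outcome, so they cannot separate a specific effect of acupuncture from a non-specific one. The third, with 50 patients, has partial masking at most.

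The conclusion rests on two assumptions: that a physician placing plasters recognizes the patient as belonging to the plaster group, and that SOC-control patients knew they were getting no procedure. Both follow from the arm descriptions. The documents give no basis for the size or direction of any resulting bias. The correction is needed, but it concerns description and interpretation and does not invalidate the randomized comparison.

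**What to change.** 1. Qualify the title, and rewrite the Blinding sentence by party and contrast. Physicians placing plasters knew who received them but not that the procedure was a sham. Acupuncturists and SOC-control patients were not blinded. Keep data collectors and the statistician as blinded, and say how collectors were kept so.
2. State that both SOC-control contrasts are open-label for patients, and base any claim of a specific acupuncture effect on acupuncture vs sham.
3. Add the adjusted acupuncture vs sham estimate with its confidence interval and p value from the existing regression, for example by changing the reference arm.
4. State whether the physicians who decided on ventilation and discharge knew the arm, before giving treatment failure and length of stay any blinding label.
5. Report the training script's description of the sham-givers as a limitation that could bias acupuncture vs sham. Recruitment ended in February 2020, so rewording the script now would misstate what was done.

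The cost is some redrafting, one fact to establish and one contrast from a model already fitted. The downside is a weaker design label and a narrower claim from the SOC-control contrasts.
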